- q. Transvaginal ultrasound with or without transabdominal ultrasound must be performed to confirm the presence of uterine fibroids and the absence of any other pathology that might be responsible for the increase in menstrual bleeding, such as uterine or cervical polyps \geq 2.0 cm, large simple ovarian cyst $>$ 4.0 cm, endometrioma(s) $>$ 4.0 cm. Results must be submitted to and uterine fibroid criteria confirmed by a central reader prior to randomization into the study. Note: Transvaginal ultrasound is required. See inclusion criterion #5 and exclusion criterion #1 for guidance as to when to perform a transabdominal ultrasound and saline or gel contrast. If transabdominal ultrasound or ultrasound with saline or gel contrast is performed at Screening, it should also be performed at Week 24.
- r. Obtain sample with an endometrial suction curette (eg, Pipelle®). Endometrial biopsy is performed at Screening 1 visit and Week 24 Visit and submitted to the central laboratory. See the Laboratory Manual for guidance on handling and shipping the biopsy sample to the central laboratory for analysis.
- s. Procedure not required at the Early Termination Visit in patients whose last dose of study drug was during Week 6 or earlier. The procedure may be done if it will aid in the evaluation of an ongoing adverse event.
- t. Bone densitometry (L1-L4, total hip, femoral neck) will be assessed during the screening period and the central results will be available prior to randomization. Schedule the test at or shortly after the Screening 1 visit. Bone densitometry should be completed prior to the Screening 3 visit and as early as possible to ensure results are available prior to randomization.
- u. Patient paper diary: Patients enter diary information on menstruation status and feminine product use starting with Screening 1 visit and ending when they receive their eDiary at the Screening 3 visit. Patient eDiary: Ensure that eDiary data collection begins at least 7 days prior to Day 1. Patients enter eDiary information on a daily basis for their compliance with study treatment starting at Baseline/Day 1, menstrual bleeding and use of feminine products for menstrual bleeding, uterine fibroid-associated pain by the Numerical Rating Scale, and use of pain medications (analgesics) starting at Screening 3 visit through Week 24 or Early Termination.

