- v. Hemoglobin: a venous blood sample must be collected each time feminine products are collected to be sent to the central laboratory conducting the alkaline hematin assessment.
- w. Patients not proceeding to the extension study who have endometrial hyperplasia or endometrial cancer on the endometrial biopsy at the Week 24/Early Termination visit will be followed and will undergo a repeat biopsy in 3 to 6 months after the Week 24/Early Termination visit (see [Section 6.7](#)). The repeat biopsy will be submitted to the central laboratory.
- x. Schedule DXA as early as possible within the Week 24/Early Termination visit window. Patients not proceeding to the extension study who have had a bone mineral density loss of $>$ 2% at the lumbar spine (L1-L4) or total hip at their Week 24/Early Termination visit relative to baseline will undergo another DXA scan at 6 (\pm 1) months after the Week 24/Early Termination visit scan to evaluate recovery and will be contacted about medications and conditions (eg, pregnancy) that might affect bone mineral density through the time of the repeat DXA scan. The follow-up DXA scan will be submitted for central reading.
- y. Patient will enter responses in a paper questionnaire at the site.
- z. The patient should be asked to bring all study drug to the clinic at each visit. Please refer to [Section 5.8](#).

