A diagnosis of uterine fibroids will be confirmed during the screening period by centrally-reviewed transvaginal ultrasound (with or without a transabdominal ultrasound). Heavy menstrual bleeding will be defined as menstrual blood loss of \geq 80 mL per cycle for 2 cycles or \geq 160 mL during 1 cycle during the screening period. Women with iron-deficient microcytic anemia and hemoglobin \geq 8 g/dL and \leq 10 g/dL during Screening must be treated with oral or parenteral iron replacement therapy. Between the Baseline Day 1 and Week 24 visits, patients will attend visits monthly (ie, every 4 weeks). At the Screening, Week 12, and Week 24 visits, patients will have an assessment of bone mineral density with dual-energy x-ray absorptiometry (DXA). An endometrial biopsy will also be performed at Screening. Another transvaginal ultrasound (with or without a transabdominal ultrasound) will be performed at Week 24, followed by a repeat endometrial biopsy. Patients will have paired baseline and end-of-treatment endometrial biopsies, independent of ultrasound results. Feminine products will be standardized and will be collected and assessed for blood loss by the alkaline hematin method. Complete blood counts and chemistries will be collected monthly and uterine fibroid volumes will be assessed at the Screening and Week 24 visits. Patients will complete daily electronic diaries (eDiary) including compliance with study treatment, menstrual bleeding, use of feminine products for menstrual bleeding, uterine fibroid-associated pain by the Numerical Rating Scale, and use of pain medication to treat pain caused by uterine fibroids. Quality of life questionnaires will be completed according to the Schedule of Activities.

Safety will be assessed throughout the study by monitoring adverse events, vital signs, physical examinations including visual acuity, clinical laboratory tests, 12-lead electrocardiograms, endometrial biopsies, and assessments of bone mineral density. Height will be measured at the Screening 1 visit and weight will be measured at specified intervals.

Samples will be collected for PK assessment of relugolix, estradiol, and norethindrone and for the pharmacodynamic assessment of luteinizing hormone (LH), follicle-stimulating hormone (FSH), estradiol, and progesterone.

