4.6. Removal of Patients from Therapy

Completion of the Week 24 defines completion of the study. Patients may withdraw consent to participate in the study and discontinue treatment at any time for any reason. Investigators or the medical monitor may remove patients from therapy under this protocol for reasons of safety and/or lack of compliance as discussed below. Patients removed from therapy for any reason will undergo the assessments for the Early Termination visit (Week 24 visit) on the Schedule of Activities and will have a Follow-up visit to assess safety approximately 30 days after the end of study drug treatment (ie, after the patient's last dose of study medication).

The following safety and/or compliance events will result in the removal of patients from therapy either permanently or until the etiology of the problem has been identified and resolved:

- Any adverse event that is intolerable to the patient and that cannot be ameliorated by the use of adequate medical intervention, or that in the opinion of the investigator or medical monitor would lead to undue risk to the patient if dosing continued;
- If it is discovered after randomization that a patient failed to meet protocol entry criteria and continued participation poses an unacceptable risk to the patient's health;
- If the following liver test abnormalities develop, study drug should be discontinued immediately with appropriate clinical follow-up (including repeat laboratory tests, until a patient's laboratory profile has returned to normal/baseline status):
 - ALT or AST > 8 x ULN; or
 - ALT or AST > 5 x ULN and persists for more than 2 weeks; or
 - ALT or AST > 3 x ULN in conjunction with elevated total bilirubin > 2 x ULN or international normalized ratio (INR) > 1.5; or
 - ALT or AST > 3 x ULN with appearance of fatigue, nausea, vomiting, right upper quadrant pain or tenderness, fever, rash and/or eosinophilia (> 5%);
- Corrected QTcF prolongation of more than 500 msec as read by a cardiologist;
- Patients who have a clinically significant decrease in visual acuity as evaluated by an ophthalmologist;

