- Patients who are, in the opinion of the investigator or the medical monitor, grossly non-compliant with the protocol's requirements. This may include < 75% compliance with the study drug for at least 2 months; not returning any feminine products despite having menstrual bleeding for > 2 consecutive cycles; missing multiple study visits; and persistent (> 2 consecutive months) with < 50% of the required number of days of eDiary completion;
- Patients whose treatment assignment has been unblinded by the investigative site will be permanently discontinued from treatment;
- If the patient becomes pregnant at any time after providing a signed informed consent form, the patient must be withdrawn immediately (see [Section 7.8](#) for information on pregnancy reporting).

Should a patient fail to attend the clinic for a required study visit within the protocol-defined window, the site should attempt to contact the patient and reschedule the missed visit as soon as possible. The site should also counsel the patient on the importance of maintaining the assigned visit schedule and determine whether the patient can and/or should continue in the study based on previous non-compliance. In cases where the patient does not return for the rescheduled visit or cannot be reached to reschedule the missed visit, the site should make every effort to regain

contact with the patient. The site should attempt at least three documented telephone calls and if necessary a certified letter to the patient's last known mailing address so that they can appropriately be withdrawn from the study with a primary reason of "Lost to Follow-up."

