6.5. Early Termination Visit and Follow-up Visit

All patients withdrawing from the study prior to Week 24 will complete an Early Termination visit. The Early Termination visit procedures are identical to those of Week 24; however, for patients whose last dose of study drug is during Week 6 or earlier, the following procedures do not need to be performed: transvaginal ultrasound (with or without a transabdominal ultrasound), endometrial biopsy, and bone densitometry. These procedures may be performed, however, at the investigator's discretion, if they aid in follow-up of ongoing adverse events.

All patients who do not wish to or who are not eligible to enroll in the extension study (MVT-601-3003), will have a Follow-up visit approximately 30 days after the last dose of study drug, or prior to the date of initiation of another investigational agent or hormonal therapy affecting the hypothalamic-pituitary-gonadal axis or surgical intervention for uterine fibroids, whichever occurs first. This visit will be used to assess safety after discontinuation of study treatment including adverse events, clinical safety laboratories, 12-lead ECG, and return of menstruation. Patients who withdraw early from this study will also undergo the Follow-up visit approximately 30 days after the last dose of study drug, or the date of initiation of another investigational agent or hormonal therapy affecting the hypothalamic-pituitary-gonadal axis or surgical intervention for uterine fibroids, whichever occurs first. Refer to the Schedule of Activities at the end of the synopsis (see [Section 1.1](#)) for individual study visit procedures during the Follow-up visit.

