7.8. Pregnancy Reporting

If any patient becomes pregnant during the study, the site must discontinue the patient from the study treatment immediately and have her return for an Early Termination visit. The investigator must inform the patient of her right to receive treatment information. If the patient chooses to receive unblinded treatment information, the individual blind should be broken and the treatment assignment provided to the patient. The study team will remain blinded to the patient's treatment assignment.

If the patient agrees, the investigator should notify the patient's primary care physician of the pregnancy and provide details of the patient's participation in the study and treatment (blinded or unblinded, as applicable).

A pregnancy is to be reported to the sponsor within 24 hours of awareness by the study site personnel, using the Pregnancy reporting forms and contact information in [Section 7.6](#). The expected date of delivery or expected date of the end of the pregnancy, last menstruation, estimated conception date, pregnancy result, and neonatal data, etc, should be included in this information, as available.

The investigator will follow the medical status of the mother, as well as the fetus, and will report the outcome to the sponsor.

7.9. Vital Signs, Physical Examinations, Clinical Laboratory Tests, Electrocardiograms, and Bone Mineral Density Measures

Section 6.8.2 details the requirements for measurement of safety parameters including vital signs, physical and gynecologic examinations, clinical laboratory tests, electrocardiograms and bone mineral density.

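### A woman who becomes pregnant on treatment, with a last dose after Week 6, must have an endometrial suction biopsy and a DXA scan at her exit visit; no pregnancy exception is stated

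*Protocol*

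**What the plan says.** All references are to the Protocol.

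- **7.8, Pregnancy Reporting:** on pregnancy, "the site must discontinue the patient from the study treatment immediately and have her return for an Early Termination visit". No procedure at that visit is waived.
- **4.6, Removal of Patients from Therapy:** "If the patient becomes pregnant at any time after providing a signed informed consent form, the patient must be withdrawn immediately". The same section sets what follows removal: "Patients removed from therapy for any reason will undergo the assessments for the Early Termination visit (Week 24 visit") on the Schedule of Activities.
- **6.5, Early Termination Visit:** "The Early Termination visit procedures are identical to those of Week 24". The one relaxation is that "for patients whose last dose of study drug is during Week 6 or earlier, the following procedures do not need to be performed", naming ultrasound, endometrial biopsy and bone densitometry. The investigator may still do them to help follow an ongoing adverse event.
- **Table 1-1 footnote s** repeats this: "Procedure not required at the Early Termination Visit in patients whose last dose of study drug was during Week 6 or earlier".
- **4.1, Overall Study Design:** "Patients will have paired baseline and end-of-treatment endometrial biopsies, independent of ultrasound results".
- **Table 1-1 footnote x:** "Schedule DXA as early as possible within the Week 24/Early Termination visit window".
- **6.6 and footnotes w and x**, for women not entering the extension: a repeat biopsy 3 to 6 months later after hyperplasia or cancer, and a repeat DXA at about 6 months after a bone density loss above 2%. Pregnancy appears there only as something to ask about because it may affect bone density.

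**The concern.** Each rule is unremarkable alone. Together they instruct a site to perform a suction-curette biopsy of the uterine cavity and a DXA scan on a woman known to be pregnant, provided her last dose fell after Week 6. Nothing in the protocol tells the site to stop.

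The first stake is the safety of the pregnancy, and the biopsy is the main hazard. The second is interpretability. Section 7.8 collects pregnancy outcome, and section 7.10 lists reproductive toxicity as a potential risk of relugolix. If a loss follows a protocol-mandated biopsy, the procedure and the study drug compete as explanations, and the few pregnancies observed become hard to read.

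**Working it through.** The point rests on how the sections combine. The plan has no figure of its own to reproduce; the arithmetic below only shows which visits the rule reaches.

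**Step 1: the chain.** Pregnancy leads to an Early Termination visit (7.8). Removal for whatever reason brings the Week 24 assessments, and pregnancy is a listed reason (4.6). Early Termination content equals Week 24 content (6.5). Week 24 includes suction-curette biopsy (footnote r, 6.8.2.6) and DXA (Table 1-1).

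**Step 2: exceptions.** The only waiver (6.5, footnote s) depends on dosing time. Sections 4.7, 6.6, 6.7, 6.8.2.6, 6.8.2.7, Table 7-2 and the footnotes to Table 1-1 contain no pregnancy exception. The ultrasound before the biopsy is not a stated stopping point, given 4.1.

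**Step 3: contrast with screening.** Section 6.2.1 places the urine pregnancy test ahead of ultrasound and biopsy and halts procedures in a woman found ineligible. No equivalent order is written for Week 24/Early Termination.

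**Step 4: which pregnancies escape.** Taking week of last dose = floor((day − 1)/7) + 1:

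| Test | Window | Relevant last dose | Week | Waived? |
|---|---|---|---|---|
| Week 4 | Day 29 ± 7 = 22 to 36 | Day 36 at the latest | floor(35/7) + 1 = 6 | Yes |
| Week 8 | Day 57 ± 7 = 50 to 64 | Day 49 at the earliest, if dosed to the day before | floor(48/7) + 1 = 7 | No |

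A pregnancy found at the Week 8 test or later is therefore outside the waiver if dosing continued to the day before. The phase 2 pregnancy described in section 2.2.4.2 was found after about 46 days on drug: floor(45/7) + 1 = Week 7, also outside it.

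**Step 5: an unrecognised pregnancy at the planned visit.** The Week 24 window opens on Day 169 − 10 = 159. The Week 20 test falls on Day 141 ± 7 = 134 to 148. A DXA on Day 159 can come 159 − 148 = 11 to 159 − 134 = 25 days after the last scheduled test before it.

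**Step 6: follow-up procedures.** Required contraception ends 30 days after the last dose (4.7). The repeat biopsy and repeat DXA fall months later, and pregnancy testing at unscheduled visits is only as needed (6.7).

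**Step 7: number of women.** With 390 women and an assumed risk over 24 weeks, 390 × 0.0025 = 1.0 and 390 × 0.02 = 7.8. These counts include pregnancies found early enough for the waiver.

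**The case against.** The strongest reply is that no competent investigator would biopsy a known pregnancy, and that the protocol does not force it. Section 10.1.1 requires conduct under whichever standard protects the participant more, section 10.2.1 allows medical judgment in an emergency, and a patient may withdraw consent at any time. The Study Reference Manual, Laboratory Manual and imaging charter are not shown and may contain a pregnancy check.

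It can also be said that:

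- the clause on ultrasound results in 4.1 concerns pairing of biopsies, so little should be read into it;
- the timing of an early DXA concerns an unrecognised pregnancy, a different problem from a known one;
- pregnancy tests are already monthly, so only their order is missing;
- the Week 12 DXA has the same ordering gap;
- the 1 to 8 count rests on an assumed range applied to all 390 women, although some need no contraception under 4.7 (tubal occlusion, vasectomised partner, abstinence), and the phase 2 pregnancy occurred at 10 mg, a dose that does not fully suppress estradiol.

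Much of this stands as a limit on size. The count is only an order of magnitude, the inference from 4.1 is light, and the Week 12 gap is real. None of it removes the instruction. General ethical clauses are not a procedure-level exception. Outside an emergency, section 10.2.1 forbids deviation without approval, so omitting the biopsy would be a protocol deviation. The safe choice should not have to be one. Nor should an unseen manual have to undo what the protocol requires.

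**Conclusion.** The concern holds. Read together, 7.8, 4.6 and 6.5 require biopsy and DXA in a pregnant woman whose last dose came after Week 6, and no current section excuses her. This is a patient-safety fault in the written rules, not a statistical error.

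The numbers are small. The 1 to 8 figure depends wholly on the assumed 0.25% to 2% and overstates the group at issue to the extent that some pregnancies would be found within the waiver. The week boundaries assume that Week 6 ends on Day 42, since the protocol does not define it. Pregnancy is nonetheless foreseeable: about 130 women take placebo for 24 weeks, and a condom alone is acceptable contraception (4.7). Confidence is high about the protocol's wording; it does not extend to what sites were told in documents not shown. The gap should be closed.

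**What to change.** In 6.5, 7.8 and footnote s, state that endometrial biopsy and DXA must not be performed in a patient with a positive pregnancy test, whatever her last dosing week. At Week 24/Early Termination, require a negative urine pregnancy test before either procedure, including when the DXA is booked ahead of the main visit. Put the same exception on the repeat biopsy and repeat DXA in 6.6 and footnotes w and x. The same amendment could sensibly apply the test-first order to the Week 12 DXA.

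The cost is a few sentences in an amendment and a urine test timed before the procedures. The loss is the end-of-treatment biopsy and bone density result for those few women.

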7.10. Benefit/Risk Assessment

Adverse drug reactions (identified risks) associated with relugolix in women include nonserious events of hot flush, headache, hyperhidrosis, and loss of bone mineral density. In this protocol, relugolix will be evaluated for its benefit on the heavy menstrual bleeding associated with uterine fibroids. Low-dose hormonal add-back therapy with estradiol and norethindrone acetate will be evaluated for maintenance of bone mineral density during treatment with relugolix.

Potential risks that may be associated with relugolix treatment in women, based on nonclinical data and data available for similar compounds, include drug interactions, cardiovascular effects (QTc prolongation), hepatic enzyme increases, PLD, reproductive toxicity, and metabolic and cardiovascular changes (insulin resistance, dyslipidemia, increased weight) with an increased risk of diabetes mellitus and possible increased risk of cardiovascular disease. Additionally, there are potential risks associated with the addition of estradiol/norethindrone acetate.

Summaries of findings from both nonclinical and clinical studies conducted with relugolix can be found in the current version of the Investigator Brochure.

The risk assessment and mitigation strategy for this protocol are outlined in [Table 7-2](#).

Table 7-2 Protocol Risk Assessment and Mitigation Strategies

Potential Risk of Clinical Significance	Mitigation Strategy	
	Impact on Eligibility	Monitoring and Withdrawal Criteria
Bone Mineral Density Reversible loss of bone mineral density is a risk of the hypoestrogenic state induced by relugolix. This risk is mitigated by the co-administration of low-dose estradiol and norethindrone acetate hormonal add-back therapy.	Exclusion criteria for a history of osteoporosis, metabolic bone disease, and prior medical therapy for low bone mineral density.	Bone mineral density will be monitored at the Baseline Day 1, Week 12, and End of Treatment visits and all fractures will be reported as adverse events.
Drug Interactions	Exclusion of co-administration P-gp inhibitors/inducers.	Collection of adverse events.

Potential Risk of Clinical Significance	Mitigation Strategy	
	Impact on Eligibility	Monitoring and Withdrawal Criteria
QTc Prolongation Negative Thorough QT/QTc clinical study.	Empiric exclusion of baseline QTcF > 470 msec.	12-lead ECG at Baseline Day 1, Week 12 and End of Treatment visits, and as clinically applicable; withdrawal for QTcF > 500 msec.
Hepatic Enzyme Increase Isolated increases in hepatic transaminases have been observed in prior clinical studies. There have been no reported cases consistent with drug-induced liver injury including an increase in bilirubin. Abnormal LFTs are considered adverse events of clinical interest in this study.	Exclusion criteria for AST and ALT > 2 x the ULN; total bilirubin values > 1.5 x ULN	Abnormal LFTs (AST or ALT > 3 x ULN) that develop during the randomized treatment period will be reported within 24 hours of study personnel awareness.
Phospholipidosis Data from nonclinical studies in rats and monkeys showed histopathological changes consistent with PLD. PLD by itself is not adverse. No clinical evidence of relugolix-related PLD-associated toxicity has been observed nor was there a clinically meaningful increase in a biomarker of PLD assessed in phase 2 clinical studies.	Patients with significant underlying medical conditions are excluded.	Routine safety monitoring including laboratory assessments, ECGs, and assessment of adverse events; visual acuity will be checked at the beginning and end of the study.
Metabolic Changes Metabolic changes (insulin resistance, dyslipidemia, and increased weight) with increased risk of diabetes are a potential risk of the hypoestrogenic state induced by relugolix.	Exclusion criteria for current medical history of cardiovascular disease.	Fasting lipids and glucose will be monitored during the study.
Reproductive Toxicity	Premenopausal compliance with specified acceptable non-hormonal contraception; exclusion of pregnant and lactating women.	Monthly pregnancy testing; immediate withdrawal for pregnancy.
Risk of Estradiol (1.0 mg)/Norethindrone Acetate (0.5 mg) Low-dose estradiol and norethindrone acetate are approved for the prevention of postmenopausal osteoporosis and the treatment of moderate to severe vasomotor symptoms. It is contraindicated for women with a history of breast cancer or	Women with breast cancer or other estrogen-dependent malignances, a history of deep vein thrombosis, pulmonary embolism, thromboembolic disease, liver dysfunction, prior	Clinical chemistries assessing LFTs, fasting glucose and lipids, and urine pregnancy tests will be performed throughout the study. Adverse events will be recorded at each visit.

Potential Risk of Clinical Significance	Mitigation Strategy	
	Impact on Eligibility	Monitoring and Withdrawal Criteria
estrogen-dependent neoplasia, history of (or active) deep vein thrombosis, pulmonary embolism, thromboembolic disease (myocardial infarction or stroke within the past year), liver dysfunction, prior hypersensitivity, and pregnancy.	hypersensitivity, migraine with aura, porphyria, and pregnancy are excluded. A mammogram, Papanicolaou test, physical examination, clinical chemistries, and 12-lead ECG will be performed prior to enrollment.	

